## Secondary Endpoint(s):

- Incidence of early post-operative complications (Surgical Site Occurrences) within 90
  days post index procedure (seroma, abscess, dehiscence, hematoma, wound
  necrosis, ileus, fistula, delayed wound healing).
- 2. Incidence of Surgical Site Infections (SSIs) within 90 days post index procedure.
- 3. Incidence of later post-operative complications occurring after 90 days post index procedure.
- 4. Incidence of hernia recurrence confirmed by clinical assessment.
- 5. Incidence of reoperation requirement due to index repair.

# Tertiary Endpoint(s):

- 1. Average length of hospital stays (LOS) post index procedure (measured in days).
- 2. Rate of opioid usage following procedure as determined by % of prescriptions filled and refilled.

#### **10.2** Sample Size Determination

Subjects from that consecutive series will be included in the study based on the defined inclusion and exclusion criteria. The planned sample size for this study will be approximately 35 treated subjects.

#### **10.3 Populations for Analyses**

**Full Analysis set (FAS):** All subjects who enroll in the study, provide informed consent waiver, and receive study intervention.

**Per-Protocol (PP) Set:** All subjects in the full Analysis Set not identified as major protocol violations (defined to be protocol violations that may have a significant impact on subject outcomes, i.e., eligibility criteria not met). This population will be clearly defined prior to data analysis.

The primary analysis will be based on the full analysis set. The per-protocol set will be supportive and will be used to assess the robustness of study results. Safety analysis will be based on the full analysis set.

#### **10.4 Statistical Analyses**

#### 10.4.1 General Approach

Descriptive statistics will be used to summarize study outcomes. For categorical data, frequency counts and percentages will be provided. For continuous data, descriptive statistics, including

T-GENVIH-002 study

Confidential

sample size, mean, median, standard deviation, and range of values (i.e., minimum and maximum values) will be provided.

All data collected in this study will be provided in subject data listings. Data collected in this study will be reported using summary tables and graphs as appropriate to the data. Descriptive summary statistics (n, mean, median, standard deviation, minimum and maximum) will be calculated for the continuous variables and/or frequencies and percentages will be produced for the categorical variables.

#### 10.4.2 Measures to Minimize Bias: Randomization and Blinding

This study does not include a randomization or blinding component. When screening subjects for the study, Investigators should offer participation to any/all patients who may meet the inclusion and exclusion.

#### 10.4.3 Analysis of the Primary Endpoint(s)

The primary endpoint for this study is descriptive statistics of the incidence of post-operative complications requiring procedural intervention within 90 days post index procedure.

### 10.4.4 Analysis of the Secondary Endpoint(s)

Descriptive statistics will be provided for the following secondary endpoints:

- 1. Incidence of early post-operative complications (Surgical Site Occurrences (SSOs)) within 90 days post index procedure (seroma, abscess, dehiscence, hematoma, wound necrosis, ileus, fistula, delayed wound healing).
- 2. Incidence of Surgical Site Infections (SSIs) within 90 days post index procedure.
- 3. Incidence of later post-operative complications occurring after 90 days post index procedure.
- 4. Incidence of hernia recurrence confirmed by clinical assessment.
- 5. Incidence of reoperation requirement due to index repair.

#### 10.4.5 Analysis of the Tertiary Endpoint(s)

Descriptive statistics will be provided for the following tertiary endpoints:

- 1. Average length of hospital stays (LOS) post index procedure (measured in days).
- 2. Rate of opioid usage following procedure as determined by % of prescriptions filled and refilled

## 10.4.6 Safety Analyses

All AEs will be coded using the Medical Dictionary for Regulatory Activities (MedDRA) and presented in by-subject listings. The number and percent of subjects experiencing any AE, any related AE, and discontinuations due to an AE will be tabulated. Treatment-emergent AEs will be tabulated (frequencies and percentages) by Preferred Term (PT) within System Organ Class (SOC). If a subject experiences more than one occurrence of the same AE, and these differ in severity and/or causality, the AE will be tabulated according to the greatest severity and nearest relationship to the device. A listing of subjects who withdraw from the study due to AEs will be presented, and the incidence of AEs leading to study discontinuation will be summarized. Deaths and SAEs will be listed should they occur.

#### 10.4.7 Baseline Descriptive Statistics

Demographic and baseline data (e.g., medical history and concomitant medication) will be listed and tabulated for those subjects who enroll in the study.

#### **10.4.8 Planned Interim Analyses**

There is no planned Interim analysis.

#### 10.4.9 Sub-Group Analyses

Subgroup analyses may be performed for surgical approach and type of the Gentrix Surgical Matrix Used.

# 10.4.10 Tabulation of Individual participant Data

All data collected in this study will be provided in subject data listings by study visit.

#### 10.4.11 Sensitivity Analyses

All data will be analyzed as they were collected in the database. Missing data will not be imputed.

# 11 Regulatory, Ethical, Compliance and Operational Considerations

#### 11.1 Informed Consent and Informed Consent Process

For this study, a waiver from the IRB was obtained for the informed consent and the informed consent process.

#### 11.2 Protocol Amendment

Investigator may not modify (amend) this clinical investigation plan without obtaining written concurrence of the Sponsor, involved Ethics Committee(s), and applicable regulatory authorities.

#### 11.3 Protocol Deviations

A Deviation is an Instance of failure to follow, intentionally or unintentionally, the requirements of the CIP. The investigator is not allowed to deviate from the CIP without first receiving approval in writing from the Sponsor.

Such deviations are documented on eCRFs and reported to the Sponsor as soon as possible.

#### **11.4 Publication Policy**

Integra LifeSciences Corporation may at any time publish the results of and information pertaining to the participating subject only to compliance with regulatory requirements pertaining to patient protected health information.

After closure of the clinical investigation, the results will be summarized in a Clinical Investigation Report, which will be submitted to the investigator, and appropriate regulatory authorities. This Clinical Investigation Report will include a summary of the results based on a statistical evaluation and clinical assessment.

The conditions under which an investigator may publish results from this study in any form are defined in detail in the clinical trial agreement.

The clinical investigation will be registered in a publicly accessible database (www.clinicaltrials.gov) prior to start of recruitment, contents will be updated throughout study conduct and results will be entered at study completion.

# 13 APPENDIX I

Table 3: List of 45Devices and SKU #

Device Name	Type:	SKU#	Size(s)
Gentrix™ Surgical Matrix (6- Layer)	PSMX	PSMX0505	5cm x 5cm
		PSMX0710	7cm x 10cm
		PSMX1015	10cm x 15cm
Gentrix ™ Surgical Matrix Plus (8-Layer)	MSPL	MSPL0507	5cm x 7cm
		MSPL0710	7cm x 10cm
		MSPL1010	10cm x 10cm
		MSPL1015	10cm x 15cm
	PSMT	PSMT1020	10cm x 20cm
Gentrix ™ Surgical Matrix Thick		PSMT1620	16cm x 20cm
		PSMT2020	20cm x 20cm
		PSMT2025	20cm x 25cm
		PSMT2030	20cm x 30cm
		PSMT3030	30cm x 30cm
		PSMT3040	30cm x 40cm

## 1. LIST OF ABBREVIATIONS

Abbreviation	Term
AE	Adverse Event
ADE	Adverse Device Effect
CFR	Code of Federal Regulations
CSF	Cerebrospinal fluid
eCRF	Electronic Case Report Form
EMR	Electronic Medical Records
FDA	Food and Drug Administration
GCP	Good Clinical Practices
ICF	Informed Consent Form
ICH	International Conference on Harmonisation
Integra	Integra LifeSciences Corporation
IRB	Institutional Review Board
LOS	Length of Hospital Stay
MedDRA	Medical Dictionary for Regulatory Activities
PMCF	Post Market Clinical Follow-up.
SADE	Serious Adverse Device Event
SAP	Statistical Analysis Plan
SAS	Statistical Analysis System
SD	Standard Deviation
SOA	Achedule of Activities
SOP	Standard Operating Procedures
SSI	Surgical Site Infection
SSO	Surgical Site Occurrence
USADE	Unanticipated Serious Adverse Device Event

#### 2. INTRODUCTION

This document provides a detailed description of the statistical methods and procedures to be implemented during the analysis of the clinical study. The methods and procedures are intended to support the generation of study report, including detailed descriptions of the populations and methodologies, as well as summary tables, listings and graphics.

This statistical analysis plan (SAP) is based on Version 1.0 of the Protocol #T-GENVIH-002.

#### 3. STUDY OBJECTIVES

The primary objective of this study is to capture existing clinical performance data to confirm the continued performance of the Gentrix® Surgical Matrix. The safety objective of this study is to capture existing Gentrix® Surgical Matrix Complication data in the immediate post-operative period of 90 days. Existing clinical data support the safety and performance of the Gentrix® Surgical Matrix. There are currently no safety concerns with these products. This clinical investigation will confirm the safety and performance of the Gentrix® Surgical Matrix and identify any unknown side-effect.

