# 1 Protocol Summary

# 1.1 Protocol Synopsis

Title	A Retrospective Analysis of the Use of Gentrix® Surgical Matrix for	
	Soft Tissue Reinforcement in Ventral Hernia Repair	
Short Title	Gentrix Ventral Hernia Repair study	
Protocol Number	T-GENVIH-002	
Study Description	The purpose of this study is to collect additional safety data and	
	demonstrate the performance of Integra Gentrix® Surgical Matrix for	
	reinforcement of ventral hernia repairs. Retrospective data will be	
	collected and assessed for early post-operative surgical site events	
	and complications in the immediate post-operative period of 90 days.	
Pre/Post-Market	Post-Market	
Product(s)	Gentrix® Surgical Matrix - (6-layer), - Plus (8-layer), and -Thick	
	*Refer to Erreur! Source du renvoi introuvable. at the end of the protocol for product-specific Stock Keeping Units (SKUs) to be included in this study.	
Indications for Use	Gentrix Surgical Matrix is intended for implantation to reinforce soft	
	tissue where weakness exists in patients requiring	
	gastroenterological or plastic & reconstructive surgery.	
	Reinforcement of soft tissue within gastroenterological and plastic &	
	reconstructive surgery includes, but is not limited to, the following	
	open or laparoscopic procedures: hernia (e.g., hiatal/ diaphragmatic)	
	and body wall repair, colon and rectal prolapse repair, tissue repair,	
	and esophageal repair.	
	Gentrix Surgical Matrix minimizes tissue attachment to the device in	
	case of direct contact with viscera.	
Study Design	Single-Arm, Retrospective, Single-Center	
Study Rationale	This study adds to the available data evaluating the safety and	
	effectiveness of Gentrix® Surgical Matrix in ventral hernia repair,	
	particularly in a real-world population.	
L		

Primary Objective	The primary objective of this study is to capture existing clinical		
	performance data to confirm the continued performance of the		
	Gentrix® Surgical Matrix.		
Safety Objective	The safety objective is to capture existing Gentrix® Surgical Matrix		
	Complication data in the immediate post-operative period of 90		
	days.		
	Gentrix® Surgical Matrix Complications are defined but not limited		
	to:		
	Seroma		
	Abscess		
	Dehiscence		
	Hematoma		
	Wound necrosis		
	Ileus		
	Fistula		
Primary Endpoint	Delayed wound healing     Incidence of post-operative complications requiring procedural		
Timary Emapoint	intervention within 90 days post index procedure.		

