## 2.3 Study & Design Rationale

This is a single-arm, single-center, retrospective study to collect in routine use additional safety data and demonstrate the performance of Integra Gentrix® Surgical Matrix for reinforcement of ventral hernia repairs. Routine use data between November 1, 2017, and present (90 days prior) will be collected retrospectively at 1 site. This study adds to the available data evaluating the safety and effectiveness of Gentrix Surgical Matrix in ventral hernia repair, particularly in a real-world population.

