#### 10.1 Statistical Hypotheses

This is a retrospective, single-arm, single center post-market study to capture existing clinical performance data to confirm the continued performance of the Gentrix® Surgical Matrix. A formal hypothesis does not apply to this study. Subjects from that consecutive series will be included in the study based on the defined inclusion and exclusion criteria.

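### The objectives promise to confirm safety and performance, but the incidence endpoints in about 35 subjects carry no criterion, comparator or confidence interval: the plan can estimate, not confirm

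*SAP*

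**What the plan says.** The stated aims are strong. SAP section 3 and Protocol 3.1 both contain the sentence "This clinical investigation will confirm the safety and performance of the Gentrix® Surgical Matrix and identify any unknown side-effect". Protocol 2.3 says the study is to "demonstrate the performance of Integra Gentrix® Surgical Matrix for reinforcement of ventral hernia repairs", and the synopsis uses the same verb. The primary objective itself, in the synopsis, Protocol 3.1 and 10.1 and SAP 3, is worded as confirming continued performance.

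The analysis is descriptive. Protocol 10.1: "A formal hypothesis does not apply to this study". Protocol 10.2: "The planned sample size for this study will be approximately 35 treated subjects"; SAP 8 gives the same number and adds that it does not rest on hypothesis testing. Protocol 10.4.1: "For categorical data, frequency counts and percentages will be provided". Protocol 10.4.3: "The primary endpoint for this study is descriptive statistics of the incidence of post-operative complications requiring procedural intervention" within 90 days. Protocol 10.4.4: "Descriptive statistics will be provided for the following secondary endpoints". SAP 9.1 rules out formal testing, SAP 9.3.1 reports the primary endpoint as a proportion of subjects, and SAP 9.3.2 summarises the secondary incidences by subject.

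For recurrence, SAP 9.2.8 adds a Kaplan-Meier curve, but describes it as covering the subjects who had a recurrence at follow-up. Follow-up lasts up to one year or less (Protocol 6.1.4). SAP 11 expects missing endpoint data and does not impute.

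**The concern.** Confirming something requires a statement that the data could contradict: a threshold, a reference rate or a comparison. Neither document sets one, so no result could fail to confirm. Nor is there an interval to show how uncertain each rate is.

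Protocol 11.4 commits to a report for regulatory authorities and to public posting of results. A report that follows the objective as worded could say that safety and performance were confirmed on the strength of a bare percentage, although the same count fits a wide range of true rates.

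The recurrence curve adds a second problem. If it is run only on subjects with a recurrence, it must end at 100% recurrence whatever the device does.

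**Working it through.** **Planned N.** About 35 cannot be reproduced: the documents give no alpha, power, expected rate, margin or precision target. SAP 8 says N is not derived from a test, so there is no derivation to call right or wrong.

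**What 35 subjects can show.** Input: n = 35 (Protocol 10.2, SAP 8). Event counts are assumed, because the plan states no expected rate. Every subject is taken as fully ascertained to day 90. The exact two-sided 95% (Clopper-Pearson) limits for x events are:

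- lower = 0.025 quantile of Beta(x, n − x + 1), or 0 if x = 0
- upper = 0.975 quantile of Beta(x + 1, n − x)

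For x = 0 the upper limit reduces to 1 − 0.025^(1/n). At n = 35 this is 1 − 0.025^(1/35) = 0.100.

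| Events / n | Observed | Exact 95% CI |
|---|---|---|
| 0/35 | 0% | 0 to 10.0% |
| 1/35 | 2.9% | 0.1 to 14.9% |
| 3/35 | 8.6% | 1.8 to 23.1% |
| 5/35 | 14.3% | 4.8 to 30.3% |

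At 5/35 the interval is 30.3 − 4.8 = 25.5 percentage points wide. Because N is approximate, the zero-event upper limit was also computed at n = 30 (11.6%) and n = 40 (8.8%). The picture does not change.

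**Recurrence curve.** Assumed data: 4 recurrences at days 120, 180, 240 and 300 among 35 subjects, 31 event-free. The Kaplan-Meier estimate is S = product of (1 − 1/number at risk) over the events; intervals use Greenwood variance on the log-log scale.

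- Only the 4 recurrences entered, as SAP 9.2.8 reads: at risk 4, 3, 2, 1, so S = 0.75, 0.50, 0.25, 0. The curve reaches 100% recurrence at day 300. This holds for any set of event times, because nobody is censored.
- All 35 entered, event-free subjects followed to day 365: at risk 35, 34, 33, 32, so S = 31/35 = 0.886 and recurrence by day 300 is 11.4% (95% CI 4.5 to 27.6%).
- All 35 entered, event-free follow-up ending evenly between days 90 and 365: at risk 31, 24, 16, 9, so S = (30/31)(23/24)(15/16)(8/9) = 0.773 and recurrence by day 300 is 22.7% (8.2 to 53.9%).

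The crude proportion is 4/35 = 11.4% in all three cases. The event times and censoring pattern are invented; they show the mechanism, not an expected result.

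**The case against.** The strongest reply is that the whole plan is openly modest. Both formal objectives are, first of all, to capture existing data, the rationale is to add to what is available, and inference is disclaimed more than once. On that reading, confirming means only checking consistency with prior evidence. A reader given n and N can also compute an interval, and the SAP defers outputs to separate table shells that were not available for this review and might contain one. This lowers the stakes but does not remove the mismatch: the verbs remain stronger than the analysis, and the SAP presents itself as the detailed description of methods yet names no interval.

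Several stronger readings are tempting and should not be drawn:

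- *That the plan offers nothing but point proportions.* This is true of the incidence endpoints only. The plan also has mean, SD, median and range for continuous data, a Kaplan-Meier curve, and adverse event tables and listings.
- *That the study claims to detect rare side-effects and cannot.* An event with a true incidence of 1% would indeed be absent from 35 charts with probability 0.99^35 = 70%. But neither document expressly claims such sensitivity. If the phrase about unknown side-effects means reporting what the charts show, the adverse event listings serve it, and the wording should say so.
- *That the descriptive design or N of about 35 is itself wrong.* A consecutive single-site series needs no hypothesis, and none is claimed.
- *That the rates must be recalculated among evaluable subjects only.* Replacing the planned denominator is debatable and can inflate the rate: 5/35 = 14.3% becomes 5/30 = 16.7% if five event-free subjects are dropped.

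**Conclusion.** The concern holds as a mismatch between claim and analysis. The incidence endpoints come without criterion, comparator or interval, so the study can estimate and describe rates but cannot confirm safety or performance. The size is best seen in the intervals: even no event in 35 leaves true rates up to 10.0% compatible with the data, and 5 in 35 leaves 4.8% to 30.3%. These figures assume full ascertainment and illustrative counts, and cover sampling error only. The literature rates in Protocol 2.1 do not fill the gap, because the plan does not use them as a benchmark.

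The recurrence curve in SAP 9.2.8, taken literally, is uninformative by construction. This may be loose drafting, but it should not be left to the programmer.

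A reader might infer that the report will claim confirmation. The documents do not say that; they leave it open. The data stay fully usable, so this is a change that should be made before analysis, not a fatal flaw.

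**What to change.** 1. **90-day endpoints (primary, surgical site occurrences, surgical site infections).** In SAP 9.1, 9.3.1 and 9.3.2 and Protocol 10.4.1, 10.4.3 and 10.4.4, specify n/N, percentage and exact Clopper-Pearson 95% CI. Keep the planned denominator (ITT in the SAP, full analysis set in the protocol) and show beside it the number of subjects whose charts do not cover day 90. A rate among evaluable subjects may be added as supportive.
2. **Recurrence.** In SAP 9.2.8, run the Kaplan-Meier analysis on all ITT subjects, censor event-free subjects at their last documented follow-up, and report a 95% CI.
3. **Wording.** In Protocol 3.1 and SAP 3, say that the study will estimate safety and performance outcomes and describe any side-effects observed. Align the primary objective (synopsis, Protocol 3.1 and 10.1, SAP 3) and the demonstration wording (synopsis, Protocol 2.3).

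The cost is one option in the SAS frequency procedure, confidence limits from a procedure already planned, and text edits in both documents; no further patients are needed. Item 2 needs a last-follow-up date for each subject. Protocol 6.1.5 lists only the exit type and the schedules name no such date, so it must be taken from visit dates in the charts. Kaplan-Meier also assumes that censoring is unrelated to outcome, which is uncertain when follow-up depends on the site's standard of care (Protocol 8), and the report should say so. The remaining price is a more modest claim.

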#### 3.1 Primary Endpoint

The primary endpoint of this retrospective study is the incidence of post-operative complications requiring procedural intervention within 90 days post index procedure.

#### 3.2 Secondary Endpoint

- 1. Incidence of early post-operative complications (Surgical Site Occurrences) within 90 days post index procedure (seroma, abscess, dehiscence, hematoma, wound necrosis, ileus, fistula, delayed wound healing).
- 2. Incidence of Surgical Site Infections (SSIs) within 90 days post index procedure.
- 3. Incidence of later post-operative complications occurring after 90 days post index procedure.
- 4. Incidence of hernia recurrence confirmed by clinical assessment.
- 5. Incidence of reoperation requirement due to index repair.

#### 3.3 Teritary Endpoints

- 1. Average length of hospital stay (LOS) post index procedure (measured in days).
- 2. Rate of opioid usage following procedure as determined by % of prescriptions filled and refilled.

#### 4. STUDY DESIGN

The Gentrix Ventral Hernia Repair study is a single-arm, retrospective, single-center, post-market study.

#### 5. STUDY PROCEDURE

This retrospective study specifically aims to collect data from the day of the index procedure, and post-operatively up to a maximum of one year or shorter as applicable. Data will be collected via medical records, study worksheets, and entered into electronic data capture system by the site.

Enrollment period will be approximately 1 month. Total duration of the study will be approximately three months.

**Table 1: Schedule of Data Collection Activities** 

Retrospective Data Collection	Screening	Index Surgery	Discharge	Follow-up Visit
Eligibility	X			
Demographics	X			
Medical history	X			
Ventral hernia details (location, size)		X		
CDC Wound Class (highest applicable class)		X		
Complications associated with Hernia(s) repair		X		
Surgery details (surgical approach, Time into procedure room, Time skin cut, Time skin closed, and Time out of procedure room)		X		
Gentrix Surgical Matrix Used (type)		X		
Intraoperative Details (Surgical Plane of Graft Placement, Graft fixation, Component Separation, Concomitant Procedure, Stoma presence (if applicable), Fascial closure)		X		
Adverse events		X	X	X
Device deficiencies		X		
Concomitant medication		X	X	X
Complete Case Report Forms (CRFs)	X	X	X	X

